7.3.1. Handling of Dropouts or Missing Data

All data will be analyzed as they were collected in the database. Missing data in general will not be imputed, limited imputation techniques if applied are described in Section 9.

7.3.2. Clinical Laboratory Tests

Both the change and the percent change from Baseline in serum liver biochemical parameters (liver function tests), serum lipids, hemoglobin levels, and platelet count will be tabulated for each evaluation timepoint. Data will be summarized for the endpoints as continuous variables. In addition, summaries of categories relative to the upper limit of normal ($\le 1 \text{ x ULN}$, 1 to $\le 1.2 \text{ x ULN}$, 1.2 to $\le 1.5 \text{ x ULN}$, 1.5 to $\le 2 \text{ x ULN}$, >2 x ULN) will be provided with shifts from baseline to post-baseline in these categories. Waterfall plots showing the percent change from baseline to Week 96 will be presented.

- Liver function tests: ALT/AST, GGT, total bilirubin, direct bilirubin, indirect bilirubin, albumin, alkaline phosphatase
- Lipids: total cholesterol, LDL-C, non-HDL-C, HDL-C, triglycerides
- Hematology: hemoglobin, platelets

The UK-MELD assessment, which is computed from clinical laboratory values, will be summarized similarly to laboratory data, although these scores will not be compared against standard laboratory reference ranges for individual laboratory assessments.

Also see Section 7.2.3, Laboratory Tests, as described in the Safety Analysis section.

7.3.3. Abdominal Magnetic Resonance

Change and percent change in liver and spleen volume and fat content will be calculated from Baseline and tabulated for each evaluation timepoint by multiples of normal. Data will be summarized for the endpoints as continuous variables. Spaghetti plots (1 line per subject) and plots of mean change in measurements over time may also be created for selected endpoints of interest. Ultrasound results will be summarized for subjects with no MRI.

7.3.4. Anthropometric Parameters

Anthropometric indicators of growth status (WFA, plus additional parameters if sufficient data are available) will be evaluated for subjects \leq 18 years of age. Weight-for-length/weight-for-stature and BMI, if computed, will be derived from data on weight and length/stature. Anthropometric parameters will be plotted on standard growth curves. Z-scores and percentiles based on the age-gender standardized norms will be calculated in accordance with the methodology described by the WHO (subjects \leq 24 months) or CDC (subjects \geq 24 months to 18 years) and using the growth charts relevant to the respective methodology. When possible, historical data on growth parameters will also be incorporated into the analyses. The growth curve will be generated for each subject. In addition, the percentages of subjects who meet criteria for under nutrition (underweight, stunting, and wasting) will be tabulated at each time point.

For subjects who are >18 years of age, BMI will be derived and summarized over time.

7.3.5. Exploratory Efficacy Analyses

Evaluation of the relationship between non-invasive measurements of liver fat content and liver histopathology may also be conducted using scatter plots and Spearman's rank correlation analysis.

7.4. Pharmacokinetic Analyses

Details of pharmacokinetic analyses will be described in a separate analysis plan.

7.5. Liver Biopsies

Data from Liver biopsies conducted will be summarized using tables and graphical displays, where applicable.

7.5.1. Ishak Fibrosis Score, Microvesicular Steatosis, Macrovesicular Steatosis, Lobular Inflammation and Portal Inflammation

These scores are reported on an ordinal scale; the Ishak Fibrosis Score ranges from 0 (No fibrosis/Normal) to 6 (Cirrhosis, probable or definite), while the other scores range from 0 to 4.

Each of the scores will be provided in a frequency table with number and percentage within each ordinal level at the timepoints specified in the Schedule of Assessments.

For each of the scores, shift tables will be used to summarize changes in categories (or levels) from Screening/Baseline to each subsequent timepoint at which biopsy data are collected.

7.5.2. Other Histopathology Variables

Percent fat, percent collagen, percent SMA and percent CD68 will be summarized as continuous variables for each timepoint as specified in the Schedule of Assessments. Observed results, the change from baseline and the percent change from baseline will be presented.

7.6. Endoscopic Biopsies

Per study protocol, endoscopic biopsy was conducted for subjects with evidence of growth abnormalities or malabsorption (Criterion 5d on List of Inclusion/Exclusion Criteria) to measure lipid substrates. Results may be summarized.

7.7. Esophagogastroduodenoscopy

Per study protocol, esophagogastroduodenoscopy (EGD) was conducted for subjects with evidence of advanced liver disease (Criterion 5a on List of Inclusion/Exclusion Criteria) to document the presence, size and quality of esophageal varices. Data may be summarized.

7.8. Subject Health-Related Quality of Life (HRQOL) Outcomes Analyses

For the subset of subjects \geq 5 years of age, change in HRQOL measures will be calculated from Baseline and tabulated for each evaluation timepoint as an exploratory analysis. In addition to the evaluation of changes in the overall scores for each HRQOL measure, changes in subscales and summary scores, as applicable to the HRQOL instrument, will be summarized.

For the PedsQLTM, in addition to the Generic Core Scale, the 4 subscales (physical functioning, emotional functioning, social functioning, and school functioning) may also be summarized. Observed measurements and changes and/or percent changes from baseline to study time-points will be summarized including 95% confidence intervals.

Summaries may be presented by subgroup.

7.9. LAL Enzyme Activity

LAL enzyme activity will be summarized using the results from the dried blood spot, if available, or alternatively the results from the whole blood. Results will be categorized as affected (<=0.016 nmol/punch/hr), carrier (0.017 to 0.026 nmol/punch/hr); and unaffected (0.027 to 0.0152 nmol/punch/hr). The number and percentage of subjects in each of these categories will be summarized for each visit at which the test was performed.

In addition, a shift from baseline will be presented showing improvement, no change, and worsening. Generally, the percentages of the shifts will be based on the number of subjects with baseline and post-baseline data. However, summaries of subjects showing improvement (i.e., affected to carrier, affected to unaffected, and carrier to unaffected) will be the number of subjects who were classified as carrier or affected at baseline and had a post-baseline result. Similarly, the summaries of subjects showing worsening (i.e., unaffected to carrier, unaffected to affected, and carrier to affected) will be based on the number of subjects who were in classified as unaffected or carrier at baseline and had a post-baseline result.

Summaries may be presented by subgroup.

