8.4. Demographics and Baseline Characteristics

Demographics and baseline characteristics, including results of DNA and LAL enzyme activity testing, will be listed for each subject and tabulated overall, according to the methods in Section 8.1. Chronological age will be reported in years to one decimal (i.e., xx.x years).

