| Carotid MRI | X | | | | | | | | | | | | | | X ^p |
| Esophagogastroduodenoscopy ⁴ | X | | | | | | | | | | | | | | X ^p |
| Endoscopic biopsy ⁵ | X | | | | | | | | X ^p | | | | | | |
| Liver Biopsy ⁶ | X | | | | | | | | | | | | | | X ^p |
| Hepatic Venous Pressure Gradient | X | | | | | | | | | | | | | | X ^p |
| Transient elastography ⁷ | X | | | | | | | | | | | | | | X ^p |
| HRQOL | X | | | | | | | | X ^p | | | | | | X ^p |
| Clinical Laboratory⁸ | | | | | | | | | | | | | | | |
| DNA Blood Sample ⁹ | X | | | | | | | | | | | | | | |
| LAL Enzyme Activity (DBS) | X | | | X ^p | | X ^p | | | X ^p | | | | | | |
| Liver Panel | X | X ^p | X ^p | X ^p | X ^p | X ^p | | | X ^p | | | X ^p | | | X ^p |
| Lipid Panel | X | X ^p | X ^p | X ^p | X ^p | X ^p | | | X ^p | | | X ^p | | | X ^p |
| Hematology, Electrolytes, Glucose, Creatinine | X | | | | | X ^p | | | X ^p | | | X ^p | | | X ^p |
| Coagulation Panel | X | | | | | X ^p | | | X ^p | | | X ^p | | | X ^p |
| Pregnancy Test ¹⁰ | X | X ^p | X ^p | X ^p | X ^p | X ^p | X ^p | X ^p | X ^p | X ^p | X ^p | X ^p | X ^p | X ^p | X ^p |
| Anti-drug Antibody | | X ^p | X ^p | X ^p | X ^p | X ^p | | | X ^p | | | X ^p | | | X ^p |
| Urinalysis | X | | | | | X ^p | | | X ^p | | | X ^p | | | X ^p |
| Macrophage Activation Markers | X | | | | | X ^p | | | X ^p | | | X ^p | | | X ^p |

| Assessments* | Screening | Treatment | | | | | | | | | | | | | | |
|--|------------------|----------------|------------------------------|---------|---------|----------------|---------|---------|----------------|---------|---------|----------------|---------|---------|----------------|--|
| | Day -45 to Day 0 | Day 0 | Week 2 | Week 4 | Week 8 | Week 12 | Week 16 | Week 20 | Week 24 | Week 28 | Week 32 | Week 36 | Week 40 | Week 44 | Week 48 | |
| | | | ±7 days | ±7 days | ±7 days | ±7 days | ±7 days | ±7 days | ±7 days | ±7 days | ±7 days | ±7 days | ±7 days | ±7 days | ±7 days | |
| HbA1c | X | | | | | X ^P | | | X ^P | | | X ^P | | | X ^P | |
| Viral Hepatitis Screen | X | | | | | | | | | | | | | | | |
| CDT | X | X ^P | | | | | | | X ^P | | | | | | X ^P | |
| Blood Exploratory Biomarkers | X | | | | | X ^P | | | X ^P | | | X ^P | | | X ^P | |
| Pharmacokinetic Profile ¹¹ | | X | | | | | | | X | | | | | | X | |
| Vital Signs ¹² | X | X ^P | Every two weeks ^P | | | | | | | | | | | | | |
| Sebelipase alfa Infusion ¹³ | | X | Every two weeks | | | | | | | | | | | | | |

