4.2. Changes from Analyses Specified in the Previous Version of the SAP

In addition to items described in Section 4.1, Changes from Analyses Specified in the Protocol, the additions, clarifications and a few deletions have been made to the previous version of the SAP.

The following additional summaries have been described in this version of the SAP:

- Additional baseline characteristics are summarized including, among others, a summary of the LAL enzyme activity and DNA results at baseline.
- The number and percentage of subjects on a modified diet at baseline and with changes in diet over the course of the treatment period are summarized.
- The number of weeks on specific doses of sebelipase alpha is summarized.
- A listing of infusion associated reactions (IARs) for those subjects with a change in sebelipase alpha dosing is added.
- Summaries of select laboratory parameters will be presented relative to the upper limit of normal (ULN).
- The summary of the Child-Pugh Status is described.
- Details of the physical examination summaries are provided.
- A shift from baseline in the interpretation of the 12-lead ECGs has been described.
- The percent change from baseline is added as a summary of each endpoint for which a change from baseline was planned.
- The United Kingdom Model for End-Stage Liver Disease (UK-MELD) summary is described.
- A summary of the post-baseline LAL enzyme activity is described.

The following clarifications have been provided to this version of the SAP:

- Medical histories are summarized separately for those identified as prior and concomitant disease.
- The Denver II assessment will be presented using the overall score and not the domain scores.
- Exploratory analyses of the effect of ADAs on the efficacy of SBC-102 will not be explored using stratified analyses. This may be added if at least 5 subjects are ADA positive at the time of the analysis.
- Laboratory abnormalities will not be specified as CS (Clinically Significant) or NCS (Not-Clinically Significant) by the Investigator or designee; instead, clinically significant changes from a subject's baseline value or previous values are recorded as AEs.

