7. STATISTICAL ANALYSIS

Alexion or designee will be responsible for data collection, reviewing and validating all the information in the eCRFs, statistical analysis, and generation of the clinical report. The final statistical analysis will not begin until the entire database is locked and signed off.

The Alexion Biostatistics Department or designee will perform the statistical analysis of the data derived from this trial. The analysis will be performed using the SAS® statistical software system Version 9.2 or higher.

No formal inferential statistical testing will be performed. As appropriate, 95% two-sided confidence intervals (CIs) will be calculated around the estimates based on the exact binomial distribution (Clopper-Pearson method) for binomial endpoints and the t-distribution for continuous endpoints. P-values and 95% confidence intervals, where presented, will be considered descriptive and will be provided to facilitate clinical review and interpretation.

All data collected in this study will be provided in subject data listings sorted by subject number; the dose of SBC-102 temporally associated with the data will be included on the listing. Summary tables and/or graphs will be presented for each endpoint, as appropriate to the data, by evaluation time point. Visits will be summarized as collected, and data collected from unscheduled visits will be included in subject listings. Unless otherwise noted, the following standard conventions will be used for creating descriptive summaries:

- Continuous numeric endpoints will be summarized by providing the number of subjects with nonmissing data, the mean and standard deviation (SD) of the data, and the minimum, first quartile (Q1), median, third quartile (Q3), and maximum value;
- For categorical endpoints, the number and percentage of subjects with each possible outcome will be displayed. The denominator for percentages will not include subjects with missing data;
- Mean, median values, Q1 and Q3 will be presented with one decimal point more than the original value, SD will be displayed with two decimal points more than the original value and minimum/maximum values will have the same number of decimal points as the original value;
- In frequency tables the percentage will be displayed with no decimal place.

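### The unaffected class for LAL enzyme activity is printed with its upper limit below its lower limit, so no result can fall in it and 5 of the 9 shift cells cannot be filled

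*SAP*

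**What the plan says.** SAP 7.9 defines three classes in nmol/punch/hr: affected at 0.016 or below, carrier from 0.017 to 0.026, "and unaffected (0.027 to 0.0152 nmol/punch/hr"). SAP 7.1.3.4 repeats these limits for the baseline table. Neither document gives any other limits for the classes.

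Two outputs in SAP 7.9 use them. Counts and percentages per class "will be summarized for each visit at which the test was performed". A shift from baseline then shows improvement, no change and worsening. Moves from affected or carrier to a higher class count as improvement, and the denominator for improvement "will be the number of subjects who were classified as carrier or affected at baseline and had a post-baseline result".

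The post-baseline table is new in this version of the plan; SAP 4.2 records that "A summary of the post-baseline LAL enzyme activity is described". Protocol 8.4 separately requires that baseline characteristics, "including results of DNA and LAL enzyme activity testing, will be listed for each subject and tabulated overall".

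The schedules in Protocol Appendix B place the "LAL Enzyme Activity (DBS)" sample at Screening, at Weeks 4, 12 and 24, and at the End of Study (Early Withdrawal) visit, for adults and children alike.

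**The concern.** The printed upper limit of the unaffected class lies below its lower limit and inside the affected class. Applied literally, the rule assigns nobody to unaffected and leaves every result above 0.026 without a class.

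This works against showing a response. A subject who moves from affected to above 0.026 has made the largest improvement the scale allows, yet cannot be counted as improved.

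Baseline can be touched too. Protocol 4.3 (criterion 3) and 5.9.6 admit transplanted subjects whose blood spot need not show the deficiency. Such a subject could have no baseline class, although the documents do not show that one enrolled.

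SAP 7.14 plans two study reports from these analyses, so an uncorrected limit could reach both.

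**Working it through.** No sample size or power figure is involved. The check applies the printed rules and counts what they can produce.

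**Inputs** (SAP 7.9; same limits in SAP 7.1.3.4)
- Affected: x ≤ 0.016
- Carrier: 0.017 ≤ x ≤ 0.026
- Unaffected: 0.027 ≤ x ≤ 0.0152

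**Step 1: is the class empty?** 0.0152 < 0.016 < 0.027, so no x satisfies both limits. On a grid from 0.000 to 0.300 in steps of 0.001 (301 values), 17 are affected, 10 carrier, 0 unaffected and 274 unclassed. Every grid value from 0.027 upward is unclassed.

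**Step 2: does reversing the limits rescue it?** No. A range of 0.0152 to 0.027 would overlap the affected class between 0.0152 and 0.016 and would contain the whole carrier class.

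**Step 3: shift table.** Three baseline classes by three post-baseline classes give 9 cells. Cells in the unaffected row or column: 3 + 3 − 1 = 5.
- Improvement: affected to unaffected and carrier to unaffected are blocked, 2 of 3.
- Worsening: unaffected to carrier and unaffected to affected are blocked, 2 of 3.
- No change: unaffected to unaffected is blocked, 1 of 3.

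**Step 4: visits.** Screening, three on-treatment weeks and the End of Study (Early Withdrawal) visit make 5 scheduled points, 4 of them post-baseline. The unaffected count is zero by construction at up to 5 visits. If the shift is shown per visit, 4 × 5 = 20 of 4 × 9 = 36 cells stay empty. If the last visit is taken as applying only to early withdrawals, a completer has 3 post-baseline points, which gives 3 × 5 = 15 of 3 × 9 = 27. The proportion is 5/9 in each case.

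**Step 5: effect on a percentage (invented counts, not trial data).** Suppose 10 subjects are affected at baseline; later 4 are above 0.026, 2 are carriers and 4 are unchanged. Intended improvement is (4 + 2)/10 = 60%. Under the printed limits it is 2/10 = 20%, or 2/6 = 33% if unclassed results are treated as missing.

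**Step 6: what was probably meant.** The lower limit of 0.027 follows directly from the carrier limit of 0.026. Of the five printed limits, only 0.0152 has four decimals. That points to the upper figure. As an illustration only, an assumed cap of 0.152 would put 126 grid values in the class and block no shift cell, but the 148 grid values from 0.153 to 0.300 would still be unclassed. An open-ended class from 0.027 would leave no upper gap. The documents do not choose between these.

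**The case against.** The strongest reply is that this is one obvious misprint with little consequence. The order of the classes is explicit, the lower limit is sound, and a careful programmer would notice the slip. The analyses are descriptive, LAL activity is in no study objective and is not a named endpoint in SAP 5.1.1 or 5.2.1, and "All data collected in this study will be provided in subject data listings sorted by subject number". If no result exceeds 0.026, no count changes. All of this stands, and it limits the weight of the point. It does not supply the missing figure: a programmer would still have to guess whether there is a cap and where.

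Several narrower objections also have force.
- The cell and visit counts all describe the same fault, and none measures an effect on data. The per-visit count depends on a display that SAP 7.9 does not specify.
- On denominators, the general convention in SAP 7 is that "The denominator for percentages will not include subjects with missing data", but it gives way where a section says otherwise, as SAP 7.9 does. A measured value above 0.026 is a result, so the more natural reading keeps that subject in the improvement denominator. The SAP does not address unclassed results, but the question disappears once the limit is corrected.
- Protocol 8.4 requires baseline activity to be tabulated but does not mention these three classes. They come from the SAP.
- Asking for no upper gap may seem to prejudge the laboratory's answer. It does not fix the limit; it asks only that any result above a stated cap be given a class.

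**Conclusion.** The concern holds. In both places the unaffected class is an empty interval, and no other text corrects it. Followed as printed, the plan leaves results above 0.026 unclassed, cannot count a rise to that level as improvement, and makes 5 of 9 shift cells unfillable.

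The conclusion about the class and the cells rests only on the printed limits. An extraction fault is unlikely because the same figures appear in running prose in two separate sections. The practical effect cannot be sized from the documents, since the number of results above 0.026 is unknown and may be zero. The plan should be corrected because a threshold for planned tables is unusable, but the point does not threaten the safety or named efficacy analyses.

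**What to change.** Before database lock, ask the central laboratory to confirm the limit for unaffected. Then correct SAP 7.1.3.4 and SAP 7.9 with identical wording so that every result falls in exactly one class. If the laboratory's range has an upper end, state which class takes results above it.

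If values are reported, or averaged for baseline under SAP 9.4.5.1, to more than three decimals, make the boundaries contiguous. For example, a mean of 0.016 and 0.017 is 0.0165, which falls between the affected and carrier limits as printed.

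The cost is one laboratory query and revised wording in two SAP sections. No new data are needed and no visit changes.

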1.4.1. Completed Study LAL-CL01

LAL-CL01, the first clinical study with sebelipase alfa, evaluated the safety, tolerability, and pharmacokinetics (PK) of sebelipase alfa following a 4-week regimen of once-weekly (qw) IV infusions of sebelipase alfa at doses of $0.35 \text{ mg}\cdot\text{kg}^{-1}$, $1 \text{ mg}\cdot\text{kg}^{-1}$, and $3 \text{ mg}\cdot\text{kg}^{-1}$ in adult subjects with liver dysfunction due to LAL Deficiency. A total of 9 subjects were enrolled into 3 sequential cohorts of 3 subjects each.

All 3 doses of sebelipase alfa were well tolerated by the subjects in this study. There were no deaths or treatment-emergent serious adverse events (SAEs), and no subject experienced an infusion-associated reaction (IAR) or discontinued treatment due to a treatment-emergent adverse event (TEAE). Most (86.4%) of the 44 reported TEAEs were considered unrelated to sebelipase alfa, and all but one were assessed by the Investigator as Grade 1 (86.4%) or Grade 2 (11.4%) in severity. One subject in the $3 \text{ mg}\cdot\text{kg}^{-1}$ dose cohort had a Grade 4 TEAE of hypercholesterolemia. Although the subject was asymptomatic, this laboratory abnormality met the definition of a Grade 4 event according to Common Terminology Criteria for Adverse Events (CTCAE), which was used to assess severity in this study.

All 3 doses of sebelipase alfa were biologically active, as evidenced by decreases in alanine aminotransferase (ALT) and aspartate aminotransferase (AST) and increases in serum lipids (total cholesterol, triglycerides, and LDL-C), which were observed within 2 and 4 weeks, respectively, and were reversible following discontinuation of sebelipase alfa therapy. Effects on serum lipids appeared more pronounced in the $3 \text{ mg}\cdot\text{kg}^{-1}$ dose cohort, whereas effects on ALT and AST appeared to be independent of dose.

PK data in adult subjects with LAL Deficiency indicate that sebelipase alfa has a short plasma half-life, ranging from 0.07 to 2.04 hours at the lowest dose of $0.35 \text{ mg}\cdot\text{kg}^{-1}$ and from 0.09 to 0.21 hours at higher doses of 1 or $3 \text{ mg}\cdot\text{kg}^{-1}$. Sebelipase alfa area under the concentration-time curve (AUC) and maximum observed concentration (C_{max}) increased proportional to dose from 0.35 to $1 \text{ mg}\cdot\text{kg}^{-1}$ and more than proportional to dose from 1 to $3 \text{ mg}\cdot\text{kg}^{-1}$.

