4.3. Inclusion Criteria

A subject must meet all of the following inclusion criteria to be eligible for this study:

1. Subject will be > 8 months of age at the time of dosing.
2. Subject or subject's parent or legal guardian (if applicable) consents to participation in the study. If the subject is of minor age, he/she is willing to provide assent where required per local regulations, and if deemed able to do so.
3. Confirmation of LAL Deficiency diagnosis as determined by the central lab; a subject who received a liver or hematopoietic stem cell transplant who does not show evidence of LAL enzyme deficiency by dried blood spot (DBS) due to the effects of transplantation must have either:
 - a. Molecular genetic testing which confirms mutations in both alleles of the *LIPA* gene (*Note: in a highly suggestive case of LAL Deficiency where only 1 mutation is identified, subjects may be included based on a fibroblast enzyme activity assay*); **OR**
 - b. Appropriately documented (based on consultation with the Sponsor) historical result of an enzyme test prior to hematopoietic or liver transplantation (performed in DBS, leukocytes or fibroblasts).
4. Subjects > 8 months but < 4 years of age at Screening will have at least 1 of the following documented clinical manifestations of LAL Deficiency:
 - a. Dyslipidemia (defined as Screening LDL-C > 130 mg/dL; TG > 200 mg/dL);
 - b. Elevated transaminases (ALT ≥ 1.5 x ULN (based on the age- and gender-specific normal ranges of the central laboratory performing the assay);

- c. Impaired growth as defined as:
 - i. WFA or SFA less than the age- and gender- appropriate 5th percentile on a standard WHO (subjects \leq 24 months of age) or CDC (subjects $>$ 24 months and $<$ 4 years of age) WFA or SFA chart for at least 3 months prior to study entry; **OR**
 - ii. Poor weight gain as evidenced by calculated weight percentile decreasing across 2 major percentile (99th, 97th, 95th, 90th, 75th, 50th, 25th, 10th, 5th, 3rd, and 1st) lines on a standard WHO (subjects \leq 24 months of age) or CDC (subjects $>$ 24 months and $<$ 4 years of age) WFA chart over a period of 6 months prior to study entry;
 - d. Suspected malabsorption with:
 - i. Persistent unexplained gastrointestinal symptoms such as nausea, diarrhea, abdominal pain, and bloating; **OR**
 - ii. Unexplained anemia, or other abnormalities suggestive of malabsorption (e.g., osteomalacia, hypoalbuminaemia, prolonged bleeding time due to vitamin K deficiency); **AND**

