5.9.3. Clinical Laboratory Collection and Analysis

Laboratory samples will be collected under the following conditions:

- Blood samples will be drawn prior to the study drug infusion on infusion visits, and in the morning (whenever feasible) on noninfusion visits;
- Subjects ≥ 18 will fast for at least 9 hours prior to collection of blood samples;
- Subjects will refrain from ingestion of alcohol for 24 hours prior to collection of blood samples for lipid and liver panels.

Refer to the SOM and Laboratory Manual for further details regarding the collection, processing, and storage of clinical laboratory samples.

A central laboratory will be responsible for analysis of all laboratory tests, with the exception of prothrombin time (international normalized ratio), activated partial thromboplastin time, urinalysis, and urine pregnancy.

Any identified laboratory abnormalities will be specified as CS or NCS by the Investigator or designee. In the event of unexplained clinically significant abnormal laboratory test results, the tests will be repeated as soon as possible (preferably within 24 hours of receiving the result) and followed up until they have returned to within the normal range and/or an adequate explanation has been identified. Clinically significant changes from a subject's baseline value or previous values will be recorded as AEs.

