| | Week 100 ±7 days | Week 104 ±7 days | Week 108 ±7 days | Week 112 ±7 days | Week 116 ±7 days | Week 120 ±7 days | Week 124 ±7 days | Week 128 ±7 days | Week 132 ±7 days | Week 136 ±7 days | Week 140 ±7 days | Week 144 ±7 days | | |
| 12-lead ECG | | | | | | | | | | | | X ^P | X | |
| Physical Examination ¹ | | | X ^P | | | X ^P | | | X ^P | | | X ^P | X | |
| Weight | Every two weeks ^P | | | | | | | | | | | | X | |
| Abdominal MRI ² | | | | | | | | | | | | X ^P | X | |
| Carotid MRI | | | | | | | | | | | | X ^P | X | |
| Esophagogastroduodenoscopy ³ | | | | | | | | | | | | X ^P | | |
| Endoscopic biopsy ⁴ | | | | | | | | | | | | | | |
| Liver Biopsy ⁵ | | | | | | | | | | | | | X | |
| Hepatic Venous Pressure Gradient | | | | | | | | | | | | X ^P | X | |
| Transient elastography ⁶ | | | | | | | | | | | | X ^P | X | |
| HRQOL | | | | | | X ^P | | | | | | X ^P | X | |
| Clinical Laboratory⁷ | | | | | | | | | | | | | | |
| LAL Enzyme Activity (DBS) | | | | | | | | | | | | | X | |
| Liver Panel | | | X ^P | | | X ^P | | | X ^P | | | X ^P | X | |
| Lipid Panel | | | X ^P | | | X ^P | | | X ^P | | | X ^P | X | |
| Hematology, Electrolytes, Glucose, Creatinine | | | X ^P | | | X ^P | | | X ^P | | | X ^P | X | |
| Coagulation Panel | | | X ^P | | | X ^P | | | X ^P | | | X ^P | X | |
| Pregnancy Test ⁸ | X ^P | X ^P | X ^P | X ^P | X ^P | X ^P | X ^P | X ^P | X ^P | X ^P | X ^P | X ^P | X | |
| Anti-drug Antibody | | | X ^P | | | X ^P | | | X ^P | | | X ^P | X | |
| Urinalysis | | | X ^P | | | X ^P | | | X ^P | | | X ^P | X | |
| Macrophage Activation Markers | | | X ^P | | | X ^P | | | X ^P | | | X ^P | X | |
| HbA1c | | | X ^P | | | X ^P | | | X ^P | | | X ^P | | |
| CDT | | | | | | X ^P | | | | | | X ^P | | |
| Blood Exploratory Biomarkers | | | X ^P | | | X ^P | | | X ^P | | | X ^P | | |
| Vital Signs ⁹ | Every two weeks ^P | | | | | | | | | | | | X | |
| Sebelipase alfa Infusion ¹⁰ | Every two weeks | | | | | | | | | | | | | |
| Adverse Event Assessment | Continuous | | | | | | | | | | | | | |
| Concomitant | Continuous | | | | | | | | | | | | | |

| Assessments* | Expanded Treatment | | | | | | | | | | | | End of Study Visit (Early Withdrawal) | Follow-up Phone Call 4 Weeks (+7) days after last infusion |

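### SAP 7.9 reports category shifts in LAL activity as improvement or worsening, but the Week 4, 12 and 24 spots are pre-infusion samples that cannot show circulating drug, and the plan does not justify a directional label

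*SAP*

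**What the plan says.** SAP 7.9 classifies each result as affected (up to 0.016 nmol/punch/hr), carrier (0.017 to 0.026) or "unaffected (0.027 to 0.0152 nmol/punch/hr", and counts subjects per band at each visit. It then adds: "In addition, a shift from baseline will be presented showing improvement, no change, and worsening". Improvement is a move towards unaffected, with subjects affected or carrier at baseline as the denominator. Worsening is a move towards affected, with subjects unaffected or carrier at baseline as the denominator. The section gives no reason for reading the moves this way and does not mention when the sample was taken. SAP 7.1.3.4 uses the same bands for the baseline table.

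On timing, Protocol 5.9.3 says: "Blood samples will be drawn prior to the study drug infusion on infusion visits". Both schedules in Protocol Appendix B place the spot at Screening and, flagged pre-infusion, at Weeks 4, 12 and 24. One more spot stands in the column headed "End of Study Visit (Early Withdrawal"; it has no pre-infusion flag and no fixed interval from the last dose.

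On kinetics, Protocol 1.4.1 reports that "sebelipase alfa has a short plasma half-life, ranging from 0.07 to 2.04 hours at the lowest dose" (0.35 mg/kg) and "from 0.09 to 0.21 hours at higher doses" (1 or 3 mg/kg).

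On transplantation, inclusion criterion 3 (Protocol 4.3) provides for a recipient "who does not show evidence of LAL enzyme deficiency by dried blood spot (DBS) due to the effects of transplantation". Protocol 5.9.6 adds that after liver transplantation the spot is taken but not used for eligibility.

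**The concern.** The three bands classify a person's own enzyme: has the disease, carries it, or neither. SAP 7.9 reuses them as a response scale. That needs a reason to expect treatment to move the spot result at the time it is drawn, and the SAP gives none. The samples are taken at the point in the dosing cycle when the least drug is present.

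Two misreadings are possible. If almost nobody changes band, the table may be taken as failure to deliver enzyme, although it was not timed to show that. If a few subjects near a cut-off change band, the table reports them as improved when ordinary measurement variation could have produced the move. With about 30 subjects planned in Protocol 4.2 (SAP 9.3 expects no more than 20), one or two such moves would be visible in the percentages.

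**Working it through.** The plan states no figure for this analysis, so there is nothing to reproduce. The check has four parts.

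**1. Time since the previous dose, in plasma half-lives.** Inputs: half-lives of 0.07 to 2.04 h at 0.35 mg/kg and 0.09 to 0.21 h at 1 or 3 mg/kg (Protocol 1.4.1); infusions every 14 days (336 h) and at least 7 days apart (168 h; Protocol 6.1); footnotes in Appendix B allow 5 days (120 h) on weekly dosing. Number of half-lives n = hours since dose / half-life; fraction left = 0.5^n.

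| Gap | Half-life | n |
|---|---|---|
| 14 days | 0.21 h (longest at the 1 mg/kg starting dose) | 336/0.21 = 1600 |
| 14 days | 2.04 h | 336/2.04 = 165 |
| 7 days | 2.04 h | 168/2.04 = 82 |
| 5 days, weekly dosing | 0.21 h | 120/0.21 = 571 |

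The 5-day gap is not paired with 2.04 h because that half-life belongs to 0.35 mg/kg, which this protocol gives only every other week. (The 5-day footnotes and the 7-day rule in Protocol 6.1 contradict each other and must be reconciled.) The floor is 82 half-lives, leaving about 1.6 × 10^-25 of the starting level. These half-lives come from nine adults. If the true value were ten times longer (assumption: 20.4 h), 7 days would be 168/20.4 = 8.2 half-lives and about 0.3% would remain, so the conclusion about circulating drug does not depend on the exact figure.

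**2. Enzyme inside cells.** The half-life is for plasma, but the spot is blood on filter paper (Protocol 5.9.6). Protocol 1.2 says that the drug is internalised by macrophages and can reach other cells through the mannose-6-phosphate receptor. No document says how long such activity lasts or whether blood cells carry it. Fraction left for assumed cell-associated half-lives:

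| Assumed half-life | After 7 days | After 14 days |
|---|---|---|
| 1 day | 0.8% | 0.01% |
| 3 days | 20% | 4% |
| 5 days | 38% | 14% |
| 7 days | 50% | 25% |

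The answer runs from nothing to a material fraction, so the documents leave it open.

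**3. Asymmetry of the labels.** Affected is the lowest band, so a subject who starts there can only stay or improve. Eligibility requires a confirmed LAL Deficiency diagnosis, so most subjects without a transplant should start there. How often variation alone yields a label depends on the assay coefficient of variation (CV), which is not given. Assume no true change, normal error, and an effective cut at 0.0165 (the midpoint between the two bands). The per-visit chance of an improved label is then the normal tail beyond (0.0165 − true value) / (CV × true value):

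| True activity | CV 5% | CV 10% | CV 15% | CV 20% |
|---|---|---|---|---|
| 0.010 | 0% | 0% | 0% | 0.1% |
| 0.013 | 0% | 0.4% | 4% | 9% |
| 0.015 | 2% | 16% | 25% | 31% |
| 0.016 | 27% | 38% | 42% | 44% |

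Example at 0.015 and 15%: (0.0165 − 0.015) / 0.00225 = 0.67, tail 25%. The problem is confined to subjects close to the cut-off, and the documents do not say how many there are.

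**4. Who can worsen.** The worsening denominator holds subjects who start as carrier or unaffected. Under inclusion criterion 3, transplant recipients whose spot is non-deficient because of the graft belong there. A change in their spot may reflect the graft, and SAP 7.9 does not separate them.

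The unaffected band, as printed in SAP 7.9 and 7.1.3.4, runs from 0.027 down to 0.0152. No value can satisfy it, and 0.0152 lies inside the affected band. No shift into or out of it can be classified until it is corrected.

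**The case against.** A reader might infer that the label carries no information about treatment: no drug is left in the blood, so every shift is assay noise and the table looks the same whether or not the drug works. The documents do not support that. Clearance from plasma does not settle what remains in cells, the assay is on blood with whole blood as the fallback, and transplantation shows that the spot result can change. A claim that the table looks the same with or without a drug effect assumes zero retention at the outset. This objection stands, and it limits the point to what part 1 shows about circulating drug.

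Importance is also limited. LAL activity is not in the efficacy lists of Protocol 3.2.1.2 or SAP 5.2.1, SAP 7.9 lies outside the efficacy section, no formal testing is planned, and every value will be listed by subject with the associated dose. Restricting a denominator to subjects who can move in that direction is the SAP's own convention (Child-Pugh in 7.2.4, ECG in 7.2.7). These points stand too. They make the matter minor and argue against insisting that the table be deleted. They do not supply the missing reason for the word improvement, and the convention fits less well here because a non-deficient spot after transplantation can reflect the graft.

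**Conclusion.** The point holds in limited form. At Weeks 4, 12 and 24 a band shift cannot come from circulating drug (at least 82 plasma half-lives, and 1600 or more at the starting regimen on schedule). Whether it can come from cell-associated enzyme is not stated, so calling it improvement is unsupported rather than shown to be wrong. The labels are one-sided for subjects who start as affected. The chance of a spurious improved label ranges from about zero well below the cut-off to roughly 27% to 44% per visit at a true value of 0.016, under assumed CVs of 5% to 20%. Transplant recipients are mixed into the worsening count, and the unaffected band cannot be applied as printed. The conclusion on circulating drug rests on the adult half-lives in Protocol 1.4.1 and tolerates a tenfold error in them. No primary or secondary endpoint depends on this table. Severity is minor.

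**What to change.** In SAP 7.9:

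- Summarise LAL activity as a continuous value with change from baseline at each visit, and report days since the last infusion. Include the End of Study / Early Withdrawal spot, whose interval from the last dose is not fixed.
- If a shift table is kept, label the moves higher, same or lower category.
- Show transplant recipients separately.
- Correct the unaffected range in SAP 7.9 and 7.1.3.4 before any band is used. The bands can then stay in the baseline table.

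This uses data already collected and changes SAP wording and one table. The cost is that the directional shift table, part of a summary newly added in this SAP version, is lost or relabelled.
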